### **Background and rationale**

Chronic rhinosinusitis (CRS) is a chronic inflammatory disease affecting the paranasal sinuses which results in symptoms of facial pain and pressure, nasal drainage and obstruction, headaches, fatigue and often disturbances in smell and taste plaguing over 40 million Americans annually. These symptoms can negatively influence productivity and is a significant driver of the over \$5.8 billion annual direct healthcare cost, making it one of the most costly chronic diseases to manage.

CRS is a syndrome that is grossly classified by the absence (CRSsNP) or presence (CRSwNP) of nasal polyps. This clinical classification is supported by immunologic differences of the diseased sinus mucosa: CRSsNP is characterized by a T helper cell type 1 (Th1) immune profile (predominant presence of neutrophils and increased IFN- $\gamma$  cytokine) while CRSwNP is characterized by a Th2 immune profile (elevated eosinophil presence and increased interleukin (IL-4, IL-5 and IL-13)). Despite sharing a similar immunologic profile, CRSwNP is a common inflammatory presentation for a number of apparently different etiologies including cystic fibrosis, aspirin exacerbated respiratory disease, allergic fungal rhinosinusitis (AFRS), and others not yet classified. There currently remains no objective means of categorizing these various CRSwNP subtypes. Consequently, all CRSwNP patients typically undergo similar non-curative treatment consisting of multiple courses of extended antibiotics and systemic corticosteroids and recurrent sinus surgeries.

Several common fungi (i.e. Aspergillus, Cladosporium, Alternaria and Penicillium species) have been associated with allergic airway diseases including asthma and CRSwNP. However, controversies continue regarding the relevance of fungal culture results from respiratory tract specimens involving a ubiquitous pathogen such as fungi. Randomized controlled trials with oral antifungals are scarce for CRS. In the asthma literature, 3 randomized prospective clinical trials have assessed the efficacy of oral itraconazole, voriconazole, posaconazole and fluconazole in patients with severe asthma with proven

fungal sensitization [1-3]. Significant improvements in both objective measures of lung function and subjective symptoms were recorded in patients receiving oral antifungals relative to patients receiving placebo [1, 3]. In contrast, a systematic review of studies evaluating antifungal therapy in nonspecific CRS patients concluded an overall lack of efficacy with either topical or oral antifungals. Based on our preliminary data, this is not surprising as only 19% of CRSsNP showed positive fungal growth vs 76% of CRSwNP (N=21 and 63, respectively). Despite the fungal presence in the sinuses of some CRSsNP patients, we found no CRSsNP patients with Th2 fungal memory (see Preliminary data). Thus, despite the ubiquitous nature of fungi, we have found that CRSwNP predicts a much higher yield of fungi from surgically acquired sinus cultures and greater presence of fungal Th2 cell memory. But even in the CRSwNP population, there is heterogeneity of evidence for immune memory to fungi. These observations suggest that airway fungi contribute to the pathophysiology of many CRSwNP, but not in CRSsNP. **This proposal aims to test the hypothesis that the addition of oral antifungal may decrease the risk of nasal polyp recurrence after sinus surgery, and provide a novel therapeutic option for fungal-sensitive CRSwNP patients.**

### Objectives

Chronic rhinosinusitis (CRS) with nasal polyps is a common clinical presentation linking a number of different etiologies and pathophysiologies. Fungus seems to play a role in a portion of patients with CRSwNP, and in these patients, antifungals may be a significant advancement to the current standard treatment. The first challenge is identifying these patients.

In preliminary work on the role of fungi in certain CRSwNP subtypes, we developed a peripheral blood based assay that detects CRSwNP patients who have developed immune memory to fungi suggesting that fungi within their sinuses may be active in the pathophysiology of their sinus inflammation. Oral antifungals have had mixed results in the treatment of non-selected CRS patients, and are more favorable in selected CRSwNP subgroups[4]. However, recent studies only classify CRS subtypes clinically, since an objective assay was not available. **This proposal utilizes our developed ELISpot assay which has a positive predictive value of 100% and a 67% negative predictive value to identify fungal-sensitive CRSwNP subgroup that are most likely to respond to oral antifungal therapy. The goal of this proposal is to determine the efficacy of an oral antifungal, itraconazole, on the recurrence of nasal polyps in CRS patients with fungal sensitivity and to identify predictive biomarkers of a positive clinical response.** Towards these goals, the following specific aims are proposed:

**Aim 1.** Determine if adding a 24-week course of oral itraconazole after sinus surgery can prevent recurrence of nasal polyps and improve scores on health assessment questionnaires in CRSwNP patients characterized by fungal IL-4 reactivity and evidence of fungi within diseased sinuses.

Despite sinus surgery, many CRSwNP patients experience recurrence of nasal polyps. There remains no clear consensus of the appropriate post-operative treatment to minimize this recurrence. Approximately 40-70% of CRSwNP patients experience recurrent nasal polyps within 1 year after surgery even with the current post-operative medical management including an extended course of oral steroids, antibiotics and saline irrigations. Using a peripheral blood based ELISpot assay evaluating Th2 cell memory for fungal antigens, we are able to identify CRSwNP patients with fungal sensitivity. **We hypothesize that this CRSwNP subtype will demonstrate positive clinical effects with post-operative itraconazole on nasal polyp recurrence rates and health status assessment.**

**Aim 2.** Determine the effect of post-operative oral itraconazole on gene expression linked to CRS inflammation and to identify genes whose expression may serve as predictive biomarker for positive clinical response to itraconazole by microarray analysis. In preliminary studies, ST2 and other genes were significantly elevated in inflamed sinonasal mucosa from CRSwNP patients as compared to healthy

controls. **We hypothesize that the expression of a number of genes will be affected by treatment of oral itraconazole after sinus surgery and expression of some genes may correlate with a positive clinical response to itraconazole.**

### **Study Design**

**AIM 1. Determine if adding a 24-week course of oral itraconazole after sinus surgery can prevent recurrence of nasal polyps and improve scores on health assessment questionnaires in CRSwNP patients characterized by fungal IL-4 reactivity and evidence of fungi within diseased sinuses.**

CRSwNP patients undergoing a medically-indicated sinus surgery are eligible for enrollment (Figure 1). Recruited patients will undergo a blood draw for an *in vitro* ELISpot assay to identify fungal-sensitive CRSwNP patients as determined by positive fungal-induced IL-4 production. Identified fungal sensitive patients will undergo their needed sinus surgery and then randomized into either a placebo or oral itraconazole group. These medications will be added to the usual post-operative saline irrigations and 9 day course of prednisone [5]. Patients will be followed for a total of 48 weeks (24 weeks while on medication and 24 weeks after treatment) with a primary outcome of recurrence of nasal polyps requiring medical intervention. Patients who develop recurrent nasal polyps will be rescued with a prednisone taper.

This study is a **randomized control trial**, in which patients and treating physicians will be blinded, designed to test whether itraconazole after surgery in fungal sensitive, fungal culture positive CRSwNP patients will have decreased rates of nasal polyp recurrence as compared to placebo treated patients (Figure 1). **The study population will come from the rhinology practice of the Department of Otorhinolaryngology where 3 rhinologists practice** (Drs. [name], [name], and [name]) as well as the rhinology practices at UTSW and UTSA. Among the 3 rhinologists of UT Houston, approximately 150 sinus surgeries are scheduled annually involving CRSwNP. Definitions of CRSwNP are based on the criteria outlined by The Rhinosinusitis Initiative[6]. Inclusion and exclusion criteria are listed in Table 1. Up to 500 CRSwNP patients undergoing a medically-indicated sinus surgery over 3-4 years will be screened and recruited to undergo peripheral blood draw that will be used in an *in vitro* ELISpot assay to identify those that are fungal sensitive. Blood from UTSA and UTSW will be shipped to UT Houston for processing. We anticipate that 80% of those screened patients will meet inclusion criteria allowing us to enroll about 400 CRSwNP patients undergoing sinus surgery. After surgery, patients will be randomized into 1 of 2 groups (1:1 ratio, stratified by presence of asthma): 1) oral itraconazole (200 mg q12 hrs) or 2) placebo for 24 weeks. Patients will be evaluated in the clinic on post-treatment weeks 2 ( $\pm$  1 week), 6 ( $\pm$  2 weeks), 12 ( $\pm$  2 weeks), and 24 ( $\pm$  3 weeks) as per the typical post-operative management protocol (Figure 2). Patients will be clinically followed for an additional 24 weeks post-treatment for recurrent nasal polyps. Therefore, patients will be followed for a total of 48 weeks after sinus surgery or until recurrent nasal polyps requiring treatment are noted.

It is current standard practice for all CRS patients to complete validated health assessment questionnaires for CRS (SNOT-22) and undergo recorded nasal endoscopic exams at each clinic visit. All medications and any treatment side effects will be recorded at each clinic visit.

Blood will be drawn on the day of surgery for the ELISpot assay and for a baseline hepatic function. Medication compliance will be assessed by counting remaining pills at each follow-up visit. A small amount of diseased ethmoid tissue at time of surgery and post-treatment (either at time of recurrent nasal polyps or completion of 24 week treatment) will be obtained and analyzed by microarray for subjects enrolled at the UT Houston site. Sinus secretions will be sampled from the ethmoid sinus cavity at time of surgery and at clinic visit when study medication is stopped for subjects enrolled at the UT Houston site.

[figure not shown]
**Study endpoints:** The primary efficacy endpoint is recurrence of nasal polyps requiring medical intervention over 48 weeks post-surgery. Nasal endoscopy will evaluate for recurrent nasal polyps and will be scored using a nasal endoscopy scoring system. Intervention for recurrent nasal polyps with prednisone will be determined clinically by the blinded treating physician. The secondary endpoints will be validated health assessment scores (SNOT-22) for CRS, nasal endoscopy scores, and qualitative and quantitative fungal cultures.

The safety endpoints will include possible adverse events associated with itraconazole (e.g., EKG changes shortness of breath, and anaphylactic reactions to itraconazole or intolerable side effects requiring the patient to stop study medication).

**Treatment blinding and randomization protocol:** Itraconazole tablets (200 mg) will be purchased from the manufacturer. Itraconazole 200 mg tablets will be crushed and compounded into a de-identified capsule; matching placebo capsules containing cellulose which will be prepared with good manufacturing practice (GMP) standard (Avicel; FMC BioPolymer, Philadelphia, PA) by Hope Compounding Pharmacy. Each volunteer will take 1 capsules, corresponding to 200 mg of itraconazole or placebo, twice daily. Patients will be stratified by presence of asthma as determined by history and positive pulmonary function test or methacholine challenge test. A randomization schedule using permuted blocks and stratified by presence/absence of asthma will be prepared using a computer-generated random number sequence. Allocation concealment will be achieved using opaque, sealed, sequentially numbered envelopes which will be held by the research coordinator in a locked filing cabinet. A calculated number of 24 weeks of itraconazole or placebo will be dispensed in prepackaged 30-day supply boxes by the Hope Compounding Pharmacy and distributed by the Research Coordinator.

Itraconazole or placebo will be taken with either orange juice, 8 ounces of cola beverage or full meal to maximize oral absorption. Since prescribed proton pump inhibitors or H2-antagonist can interfere with itraconazole absorption, these medications will be taken midday if needed.

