**Figure 1.**

**Figure 2.**

[figure not shown]

TABLE 1	
Inclusion	
 
18-75 years old, Sinus symptoms for <math>\geq</math>12 weeks and nasal polyps noted on nasal endoscopy or CT, undergoing medically-indicated sinus surgery for CRS
 
Nasal polyps noted at time of surgery
 
Positive ELISpot assay and evidence of fungi within diseased sinus cavities
 

Exclusion	Pregnant, Autoimmune disease, cystic fibrosis, Aspirin exacerbated respiratory disease, chronic disease such as uncontrolled diabetes, cancer or HIV, history of liver or kidney disease that have effects on immune system

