## Statistics

### Power analysis

This is a pilot study focused on estimating a range of plausible treatment effects. We anticipate enrolling **500 patients over a 3-4 year period** with an anticipated 15% dropout rate. A total of 340 subjects should

Table 2

Recurrence Rates		Power	Power
Placebo	Treatment	N=320	N=102
50%	20%	1.00	0.86
50%	25%	0.99	0.68
50%	30%	0.93	0.46
50%	35%	0.61	0.26

be available for final analyses. However, we also performed a power analysis should the number of possible patients be as low as 120 patients over the 3 years with similar 15% drop rate for possible N=102. Although the goal of this study is to estimate an unbiased treatment effect, we calculated power (Table 2) to detect a range of effect sizes (as reported in the literature) assuming a two-sided test with alpha of 0.05 and N=320 and 102. The study would have adequate power to detect a large effect size. The planned complementary Bayesian analyses will provide probabilities of clinically important treatment benefits to guide the conduct of future trials.

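### The 80% eligibility yield behind 400 enrolled and 340 evaluable exceeds the plan's own 76% fungal-growth rate, which is only one part of a joint inclusion criterion

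*Combined protocol and SAP*

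**What the plan says.** The recruitment chain has three links.

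- **Screening** (Study Design): "Up to 500 CRSwNP patients undergoing a medically-indicated sinus surgery over 3-4 years will be screened and recruited to undergo peripheral blood draw". The blood is for the ELISpot, so the 500 are counted before the assay result is known.
- **Yield** (Study Design): "We anticipate that 80% of those screened patients will meet inclusion criteria allowing us to enroll about 400 CRSwNP patients undergoing sinus surgery". No derivation of the 80% is given.
- **Evaluable** (Power analysis): "with an anticipated 15% dropout rate. A total of 340 subjects should" be available for the final analyses. A low case of 120 patients, giving N=102, is also stated.

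The criteria behind the yield are as follows.

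- Table 1 lists as one inclusion item: "Positive ELISpot assay and evidence of fungi within diseased sinus cavities". The Aim 1 statement repeats both conditions, and Study Design describes the target population as "fungal sensitive, fungal culture positive CRSwNP patients".
- Table 1 and Study Population also exclude patients with, for example, aspirin exacerbated respiratory disease, recent smoking, liver disease or EKG abnormalities. The itraconazole risk section adds a list of contraindicated drugs.

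The relevant preliminary data are these.

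- Background: "only 19% of CRSsNP showed positive fungal growth vs 76% of CRSwNP", the latter from 63 patients. The same section says that immune memory to fungi varies within CRSwNP.
- Objectives: the ELISpot has a "positive predictive value of 100% and a 67% negative predictive value". The reference standard is not stated, and neither is the proportion of CRSwNP patients who test positive.

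**The concern.** The anticipated yield on the full set of criteria (80%) is higher than the reported rate of one required component (76%). The remaining requirements can only lower it. The 400 and 340 are the plan's headline size, and they rest on the 80%. If the yield is lower, a reader who relies on 340 is misled about the precision and power to expect. Table 2 gives nothing between N=320 and N=102 to show what a middling yield would mean.

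**Working it through.** **1. Reproduce the plan's figure.** 500 × 0.80 = 400, and 400 × (1 − 0.15) = 340, an exact match. Without the 80% step, 500 × 0.85 = 425, so 340 depends on it. The low case also reproduces: 120 × 0.85 = 102.

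**2. Ceiling from fungal growth alone.** P(ELISpot positive, fungi present and not excluded) ≤ P(fungi present) = 0.76.

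- Randomised: 500 × 0.76 = 380.
- Evaluable: 380 × 0.85 = 323, which is 5% below 340.
- To reach 400, the share of fungus-positive patients who pass everything else would have to be 0.80 / 0.76 = 105%, which is impossible.

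**3. Precision of the 76%.** 76% of 63 is about 48/63. The exact 95% interval is 64% to 86% (Wilson 64% to 85%). An 80% rate of fungal growth is therefore not ruled out. Even at the upper limits, a joint yield of 80% needs 0.80 / 0.86 = 93% (or 0.80 / 0.85 = 94%) of fungus-positive patients to be ELISpot positive and free of every exclusion.

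**4. Range for the unstated pass rate.** The share of fungus-positive patients who pass the ELISpot and the exclusions is not given, so the values below are assumed. Power is for a two-sided 0.05 test with 1:1 allocation and continuity correction, with n = N/2 per arm and p̄ the mean of p₁ and p₂:

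Φ{[|p₁ − p₂| − 1/n − 1.96√(2p̄(1 − p̄)/n)] / √[(p₁(1 − p₁) + p₂(1 − p₂))/n]}

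This formula reproduces the N=102 column of Table 2 (0.856, 0.677, 0.459, 0.263 against the printed 0.86, 0.68, 0.46, 0.26).

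| Assumed pass rate | Randomised | Evaluable | 50 v 20 | 50 v 25 | 50 v 30 | 50 v 35 |
|---|---|---|---|---|---|---|
| 100% (ceiling) | 380 | 323 | 1.00 | 1.00 | 0.95 | 0.75 |
| 90% | 342 | 291 | 1.00 | 0.99 | 0.92 | 0.70 |
| 80% | 304 | 258 | 1.00 | 0.98 | 0.89 | 0.64 |
| 70% | 266 | 226 | 1.00 | 0.97 | 0.84 | 0.57 |
| 50% | 190 | 162 | 0.98 | 0.88 | 0.69 | 0.42 |

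At N=340 the same formula gives 0.96 for 50% v 30% and 0.77 for 50% v 35%.

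**5. Illustration from the predictive values.** Assume that PPV 100% and NPV 67% were measured against sinus fungal growth at 76% prevalence. With ELISpot-positive share x, 0.76 = 1.00x + 0.33(1 − x), so x = (0.76 − 0.33) / 0.67 = 0.642. With PPV 100%, x is also the joint rate. Then 500 × 0.642 = 321 randomised and 321 × 0.85 = 273 evaluable, before exclusions. With the upper Wilson limit of 85% in place of 76%, x = (0.85 − 0.33) / 0.67 = 0.78.

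**6. Against the printed power.** Recomputed power at N=273 is 0.999, 0.99, 0.91 and 0.67. The printed N=320 column is 1.00, 0.99, 0.93 and 0.61. The printed 0.61 does not itself reproduce at N=320 (0.74 by this formula), which is a separate matter.

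**The case against.** **The documents' only usable figure costs little.** 323 is close to 340 and still above the N=320 used in Table 2. This stands. A reader might infer that the stated power is not delivered, but the documents do not support that. Even at N=273, three of the four printed N=320 values are met to within rounding or exceeded, and the fourth is 2 points lower. The power section claims adequacy only for a large effect.

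**Everything below 323 is assumption.** This stands too. A reader might take 273 as the expected size, but that needs a reference standard the plan does not state. Objectives presents the assay as identifying fungal-sensitive patients, which need not mean fungal growth. A further percentage for exclusions would also lack a source, and it could double-count: Study Population and Ethics suggest that patients are approached only if they already meet the criteria, so some exclusions may precede the count of 500.

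**76% is imprecise.** True, and 80% lies inside its interval. That rescues a culture-only yield of 80%, but a joint yield of 80% needs near-complete ELISpot positivity as well, for which no evidence is offered.

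**Fungal evidence may not be a condition.** The opening of Study Design and the blood-draw and randomisation parts of Study Procedures randomise on ELISpot alone. What counts as evidence of fungi is also undefined; PCR of swabs is described, but only for the Houston site. If fungal evidence is not a condition, 76% is not a ceiling. That reading conflicts with Table 1, however, and still leaves the 80% without support, because no ELISpot positivity rate is given.

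**The plan hedges.** It says up to 500, calls itself a pilot, and gives an N=102 case that needs only 120/500 = 24% yield. This is a partial hedge on the range. It does not support 400 or 340.

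**Conclusion.** The concern holds in a limited form. The arithmetic from 500 to 340 is correct; the 80% that feeds it is not supported. If both a positive ELISpot and fungal growth are required, as Table 1 and the description of the target population indicate, the plan's own point estimate caps the yield at 76%: at most 380 randomised and 323 evaluable, against the stated 400 and 340. The plan says enrol rather than randomise, but 340 is 400 less dropout, so 400 serves as the randomised base.

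The true shortfall is larger by an unknown amount, because the ELISpot positivity, joint and exclusion rates are all missing. The 321 and 273 are an illustration under an unverified reference standard, not an estimate. The finding does not show that the trial is underpowered for large effects. The cap rests on 63 patients and on reading the fungal-evidence criterion as growth.

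**What to change.** 1. In Study Design, replace the 80% and the 400 with a yield derived from the observed rate of patients who are both ELISpot positive and fungus positive, after exclusions. On current data this is no more than 76%. State the ELISpot positivity, joint and exclusion rates, with their denominators, and say which exclusions are applied before the 500 are counted.
2. In the power section, replace 340 with the resulting N and a range that reflects the uncertainty in those rates, and show power across that range in Table 2. The section also words the 500 as enrolled where Study Design words them as screened; use one term.
3. Reconcile Table 1, Study Design, and the blood-draw and randomisation parts of Study Procedures on whether fungal evidence is a condition for randomisation, and define what counts as such evidence at all three sites.

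The cost is wording, a revised table and a somewhat less favourable stated size. No extra enrolment is needed.

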#### **Patient Withdrawal from Study**

Patients are free to withdraw from the study at any point in the study. In addition, patients can be withdrawn from the study by investigators if patients do not fulfill inclusion criteria, meet exclusion criteria, develop any complications from administered medications, and/or develop recurrent nasal polyps requiring medical or surgical intervention.

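### Follow-up ends at the first treated recurrence, so later SNOT-22 and endoscopy scores come only from non-recurrers and the questionnaire half of Aim 1 can be biased

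*Combined protocol and SAP*

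**What the plan says.** Aim 1 (Objectives) asks whether itraconazole after surgery "can prevent recurrence of nasal polyps and improve scores on health assessment questionnaires in CRSwNP patients". The study endpoints paragraph of Study Design then lists: "The secondary endpoints will be validated health assessment scores (SNOT-22) for CRS, nasal endoscopy scores, and qualitative and quantitative fungal cultures".

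Three statements bear on what happens after a recurrence, and they do not agree:

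- The opening of Study Design gives 48 weeks of follow-up (24 on medication, 24 after) with no exception. It adds: "Patients who develop recurrent nasal polyps will be rescued with a prednisone taper".
- Later in Study Design, the rule is that "patients will be followed for a total of 48 weeks after sinus surgery or until recurrent nasal polyps requiring treatment are noted".
- Patient Withdrawal from Study lets investigators withdraw patients who "develop recurrent nasal polyps requiring medical or surgical intervention". The wording is permissive, and it does not separate stopping study drug from leaving follow-up.

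Study Design describes SNOT-22 as standard at each clinic visit and says that patients "undergo recorded nasal endoscopic exams at each clinic visit". The readable text names visits at weeks 2, 6, 12 and 24. It names no visit week between 24 and 48, although Figure 2 is not shown. For the scores, the document gives no analysis time point, model, estimand, rescue handling or missing-data rule.

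**The concern.** The primary event decides who goes on being measured for the secondary endpoints. Once recurrences begin, the scores still being collected come from placebo patients who have not recurred and itraconazole patients who have not recurred. Randomisation does not protect that comparison, because treatment is expected to affect who remains.

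If the drug works on polyps, placebo loses more of its more severe patients, and the remaining groups are more alike than the arms as randomised. The trial could then report fewer recurrences with little apparent symptom benefit, partly because of the follow-up rule. This differs from the 15% dropout in Power analysis: the loss is built into the design and tied to outcome. Scores that were never collected cannot be recovered by analysis. Power analysis describes the trial as a pilot whose goal is an unbiased estimate of treatment effect, so a distorted symptom estimate matters even without a formal test.

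**Working it through.** **The plan's own figures.** None is given for SNOT-22 or endoscopy. Table 2 covers power for recurrence only. A two-sided continuity-corrected comparison of two proportions, with N/2 per arm, reproduces seven of its eight cells within 2 percentage points. The exception is N=320 at 50% vs 35% (stated 0.61, recomputed 0.74). It does not bear on this point, which uses only the recurrence rates.

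**Step 1: how many patients lose later scores.** Inputs from Power analysis and Study Design: placebo recurrence 50%; treatment 20%, 25%, 30% or 35%; 1:1 allocation. Patients still scored = n per arm × (1 − recurrence rate).

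- N=320 (160 per arm): placebo 160 × 0.50 = 80; itraconazole 160 × 0.65 = 104 to 160 × 0.80 = 128.
- N=102 (51 per arm): placebo about 26; itraconazole about 33 to 41.

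These are week-48 losses, before other dropout. At week 24 only earlier recurrences are missing, and the document gives no split by time.

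**Step 2: what selection could do (assumed model).** Let recurrence occur when a normally distributed severity exceeds a threshold. Placebo severity is N(0,1) with threshold 0, which gives 50%. Itraconazole severity is N(−d,1) with d = −z(p), where p is its recurrence rate. Treatment acts on the score only through severity, and rescue is ignored.

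- Placebo non-recurrer mean: −φ(0)/0.5 = −0.798.
- Itraconazole non-recurrer mean: −d − φ(d)/(1 − p).

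| Recurrence, placebo vs itraconazole | All-patient difference d | Itraconazole non-recurrer mean | Difference among non-recurrers | Share retained |
|---|---|---|---|---|
| 50% vs 20% | 0.842 | −1.192 | 0.394 | 0.468 |
| 50% vs 25% | 0.674 | −1.098 | 0.300 | 0.445 |
| 50% vs 30% | 0.524 | −1.021 | 0.223 | 0.426 |
| 50% vs 35% | 0.385 | −0.955 | 0.157 | 0.408 |

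These are severity units, not SNOT-22 units. If the score has correlation ρ with severity, both differences are multiplied by ρ and the share retained is unchanged. The document gives no ρ. Over an assumed 0.3 to 0.7, the shift against itraconazole, ρ × [0.798 − φ(d)/(1 − p)], runs from 0.07 SD (ρ = 0.3, 35%) to 0.31 SD (ρ = 0.7, 20%). It is zero if ρ = 0 or the recurrence rates are equal.

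**Step 3: an example in score units.** Take 50% vs 30%, ρ = 0.5, N=320, two-sided alpha 0.05, score SD 1.

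- All patients: difference 0.262; standard error √(2/160) = 0.112; power 0.65.
- Non-recurrers: difference 0.112; standard error √(1/80 + 1/112) = 0.146; power 0.12.

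**Step 4: allowing for rescue.** Suppose prednisone gives recurrers a lasting score gain of r SD (assumed; the document gives none). For the same example, the contrast in all randomised patients including post-rescue scores is 0.262 − (0.50 − 0.30)r. At r = 0.75 this is about 0.11, the same as among non-recurrers. Against this target, selection dilutes the effect only while r is below about 0.45 SD (ρ = 0.3), 0.75 SD (ρ = 0.5) or 1.05 SD (ρ = 0.7).

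**The case against.** A reader might infer that the questionnaire comparison is biased toward no effect as a matter of fact. The document does not support that. The direction needs four conditions: itraconazole lowers recurrence; recurrers score worse; the analysis uses only observed scores; and the target leaves out the benefit of rescue. The first is the trial's hypothesis and the second is plausible, but the document settles neither of the others. If the drug cuts recurrence and has no effect on scores, the bias moves away from zero and makes itraconazole look worse.

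Other limits also stand. Scores are taken at each clinic visit, so the recurrence visit itself is scored, and a mixed model or carried-forward value could use it. That score falls at a different time for each patient, however. Using it relies on untestable assumptions about later scores, and no such analysis is planned. The 50% and 20-35% losses apply at week 48, while named visits stop at week 24. The model is a strong case: any symptom effect outside the severity path would not be attenuated in this way. Post-rescue scores can dilute the contrast as much as selection does. Withdrawal on recurrence is only permitted, not required.

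These objections limit the certainty and the size. They do not restore the missing scores: the follow-up rule in Study Design is not permissive, and nothing else in the document requires scoring after recurrence.

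**Conclusion.** The point holds as a design flaw with a conditional direction. The written rule lets the primary event remove patients from the secondary scores, so the questionnaire half of Aim 1 can be biased. Under the trial's own hypothesis, with worse scores in recurrers and a comparison of observed scores, dilution is the expected result.

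The loss of up to 50% of placebo against 20-35% of itraconazole patients is an upper bound, reached only at week 48. The 41-47% retained is an illustration that depends on the whole effect running through recurrence severity and on ignoring rescue. It should not be read as an estimate for SNOT-22. The primary endpoint is unaffected. The change should be made because it concerns data collection and cannot be made at the analysis stage.

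**What to change.** Reconcile the two follow-up statements in Study Design with Patient Withdrawal from Study, so that recurrence fixes the date of the primary event but does not end follow-up. State separately what stops study drug and what ends study participation. Rescue care need not change.

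Continue SNOT-22 and endoscopy scoring at the standard clinic visits to week 48 in all randomised patients, name the visits after week 24, and record rescue prednisone. Compare all randomised patients by arm at a stated time point, with a stated estimand for rescue and a rule for missing scores. One option is to include post-rescue scores in the main analysis, with a sensitivity analysis using the recurrence-visit score.

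The cost is protocol wording plus some added data collection after recurrence and in weeks 24-48. It should be modest, since both assessments are described as standard at clinic visits, but the readable text schedules no visits in that later period. Post-rescue scores include the prednisone effect, which may itself narrow the difference between arms; this must be stated when results are interpreted.
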